### ***Statistical Analysis***

Characteristics of enrolled patients will be summarized using means [standard deviations] and medians [interquartile ranges] for continuous variables, and frequencies (percentages) for categorical variables. Exploratory data analyses including histograms, Pareto charts, scatter plots, and box plots will be further used to show the distribution. Appropriate transformations and estimation procedures will be performed as necessary. To test the effect of securement strategies on each of aims, we will further use Cox proportional hazard regression models for time-to-event outcomes and logistic regression models for binary outcomes. P-values of less than 0.05 will be considered statistically significant. Analysis will be conducted using SAS 9.4.

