While some evidence supports the use of tissue adhesives for securement, further randomized controlled trials are needed to assess the effectiveness of this intervention. Further, only one prospective, randomized trial evaluated patients in the emergency room setting. Nearly 50% of all hospital admissions start in the emergency department (ED) and 80% of hospitalized patients require IV access. This highlights the importance of understanding the impact of tissue adhesives on peripheral IV survival for patients admitted through the ED. While Bugden found that skin glue reduced IV failures for patients hospitalized from the

ED, patients were only followed for 48 hours. The general consensus is to continue using IVs as long as there is no clinical indication for removal. As the average hospital length of stay in the United States is 4-6 days, it is clear that the 48 hour cutoff is a critical flaw in the analysis and further investigation over a longer time period is urgently needed.

We propose a prospective randomized controlled trial to evaluate peripheral IV failure with ED patients that are hospitalized comparing securement with standard securement plus Adhezion Biomedical SecurePortIV™ to standard securement.

**Specific Aim 1:** Test the prediction that the experimental securement solution of standard dressing plus Adhezion Biomedical SecurePortIV™ will have a lower probability of failure compared to the control standard of care securement.

For Aim 1, an improved survival of the experimental securement solution will be evaluated by functionality of catheter for intravenous therapy prior to patient discharge. The event is failure of functionality identified during follow-up assessment during hospitalization. Duration of dwell and functional failure of the catheter will be employed to estimate catheter survival.

**Specific Aim 2:** Determine the difference in cause-specific IV failure rates between the experimental and control groups. Specific etiologies to be evaluated include dislodgment, infection, phlebitis, and occlusion.

**Specific Aim 3:** Determine the difference in costs associated with the experimental group versus the control group. Cost calculation will include all costs of placement in each group: labor and material.

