## **Study Design:**

We propose a prospective, single-site, parallel, two-arm randomized investigation of catheter survival when securement strategies are evaluated. Specifically, conventional securement with polyurethane dressing and tape will be compared with experimental securement with tissue adhesive, polyurethane dressing and tape. The primary objective of this study is to demonstrate that there is better survival of the catheter securement with the tissue adhesive. Exploratory secondary and adjusted multivariable analyses will also be conducted.

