**Exclusion Criteria:**

1. Patients with ultrasound-guided IV insertions
2. Alternate site of cannulation
3. Voluntary withdrawal
4. Patients with a non-standard polyurethane dressing
5. Known allergy to cyanoacrylate or formaldehyde

The survival analysis will only be performed on patients that have an IV dwell time greater than 48 hours. Over 85% of patients admitted to a progressive floor have length of stay greater than 48 hours. The sample size calculation reflects an assumed 10 - 15% exclusion rate.

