A tourniquet may be applied as needed. If the patient is actively receiving an infusion, the drip will briefly be halted to evaluate for functionality. Functionality will be assessed with the existing dressing in place. If the catheter is functional and free of any signs of complications, study subjects will be randomized by a computer generated 1:1 envelope system to either the control group: polyurethane dressing + clear tape or the experimental group: polyurethane dressing + clear tape + tissue adhesive. If the IV is not functional, a new catheter will be inserted in a new location, documented, and patient continues in the study. For the control group, the polyurethane dressing will be gently removed. Dressing will be removed carefully to minimize any potential dislodgments or skin injury. The site will be evaluated for oozing or blood and as needed cleaned with sterile gauze. Once the site is completely dry, a new polyurethane dressing will be applied and reinforced with tape in a standard fashion. See Appendix A for pictures depicting standard dressing application with tape. Once securement is complete, functionality will be reassessed per protocol above. For the experimental group, the existing securement will be gently removed. The site will be evaluated for oozing or blood and as needed cleaned with sterile gauze. Once the site is completely dry, the tissue adhesive will be applied per directions in Appendix B. A new standard polyurethane dressing will be applied and tape will be applied per the standard approach. Once securement is complete, functionality will be reassessed per protocol above. The time of the new dressing application will be noted as time zero. Catheter dwell time will begin at this point.

Additional data variables collected at the initial assessment include: demographics such as age, sex, INR > 1.5, platelets < 50, insertion site details, hours from insertion to recruitment, inserter credentials.

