### ***Follow-up Assessment:***

After initial assessment, the catheter will be assessed by the research team every 24 +/- 5 hours as long as the patient is hospitalized up to 7 days or 168 hours. At each follow up interval the researcher notes the date/time of evaluation and assesses for any signs and symptoms of complications and functionality of the device. A catheter is functional if the IV flushes without resistance. Catheters will be assessed daily for signs and symptoms of complications. See Appendix C for details regarding the assessment for complications. Any signs or symptoms of complications or lack of functionality will be reported to the patient's primary care team so that management of the IV catheter can be addressed. If the catheter and adhesive are removed early due to catheter failure or complication, or for patient discharge prior to 7 days a medical adhesive remover may be used.

If the catheter was identified to have any signs or symptoms of complications during follow-up assessment the date and time of observation of the complication will be documented in the data collection tool and the primary team will be notified of the complication. If the catheter was removed prior to the follow-up assessment then the IV removal time and the reason for removal will be obtained through chart review. For all catheters removed due to a complication, re-insertion attempt data will be tracked through the medical record in the nursing section for venous lines and need for reinsertion of the IV or escalation to a midline, PICC, or CVC will be noted. If the patient is discharged prior to the time of follow-up assessment then the time of discharge will be documented and the IV will be presumed functional until time of discharge unless otherwise noted in the chart.

The medication administration record will be queried for all medications given through each catheter with specific attention to antibiotics and anticoagulants. Vesicants/irritants that are generally given via central line or considered caustic to the vessel will be noted in both groups. Number of doses will be recorded. See Appendix D for full list of non-neoplastic vesicants.

Additional data gathered by research staff on follow-up evaluation includes: dwell time in days/hours, hospital length of stay, and number of peripheral IVs for duration of stay.

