### Appendix E: Follow Up:

| Day | Functional
1: draw
2: flush
3: infusing
4: failed | Removal
Time | Reason for
Removal | Signs/Symptoms
of Complications | Rescue
Device
1. PIV
2. USPIV
3. CVC
4. PICC
5. Midline
6. IO | Discharge <48hrs
from insertion (if
yes, remove
patient from
study) | Research
staff
initials |
|-----|---|-----------------|-----------------------|------------------------------------|--|---|-------------------------------|
| 1   |   |                 |                       |                                    |  |   |                               |
| 2   |   |                 |                       |                                    |  |   |                               |
| 3   |   |                 |                       |                                    |  |   |                               |
| 4   |   |                 |                       |                                    |  |   |                               |
| 5   |   |                 |                       |                                    |  |   |                               |
| 6   |   |                 |                       |                                    |  |   |                               |
| 7   |   |                 |                       |                                    |  |   |                               |
| 8   |   |                 |                       |                                    |  |   |                               |
| 9   |   |                 |                       |                                    |  |   |                               |
| 10  |   |                 |                       |                                    |  |   |                               |

Reasons for Removal: (1) completion of therapy (2) infiltration (3) phlebitis (4) dislodgement (5) oozing fluid/blood (6) purulent drainage (7) occlusion (8) removed by patient (9) site changed (10) other

| Day | Medications transfused via catheter |
|-----|-------------------------------------|
| 1   |                                     |
| 2   |                                     |
| 3   |                                     |
| 4   |                                     |
| 5   |                                     |
| 6   |                                     |
| 7   |                                     |
| 8   |                                     |

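### One Cox hazard ratio does not by itself show both whether the adhesive helps overall and whether any benefit continues past 48 hours

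*Combined protocol and SAP*

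**What the plan says.** The Background/Scientific Rationale section faults the earlier emergency-department trial for stopping at 48 hours: "the 48 hour cutoff is a critical flaw in the analysis and further investigation over a longer time period is urgently needed". The Follow-up Assessment section accordingly has catheters checked "every 24 +/- 5 hours as long as the patient is hospitalized up to 7 days or 168 hours". The Study Design section sets the aim: "The primary objective of this study is to demonstrate that there is better survival of the catheter securement with the tissue adhesive".

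On analysis, the Statistical Analysis section states that "we will further use Cox proportional hazard regression models for time-to-event outcomes", with logistic models for binary outcomes. It names no survival curve, proportional-hazards check, time-varying effect or estimate at a given hour.

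Two rules bear on who enters that model. The Exclusion Criteria section ends with: "The survival analysis will only be performed on patients that have an IV dwell time greater than 48 hours". The follow-up form in Appendix E has a different column: "Discharge <48hrs from insertion (if yes, remove patient from study". Dwell runs from re-dressing, per the Initial Assessment section: "The time of the new dressing application will be noted as time zero. Catheter dwell time will begin at this point". The form counts from insertion, which may be up to 8 hours before enrolment.

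**The concern.** The earlier trial had already reported fewer failures up to 48 hours, so the new information is what happens over the longer window. A single proportional-hazards ratio assumes one effect throughout and does not report when the benefit arises. A benefit that ends at 48 hours, one that starts there and a steady one are different answers for a hospital deciding whether to adopt the adhesive.

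The two inclusion rules make this worse, because they give the ratio different meanings. Take a catheter dislodged at 30 hours in a patient who stays five days. The dwell rule drops it and the discharge rule keeps it. From the plan alone, a reader cannot tell whether the reported ratio will be a blend of both periods or a late-only comparison.

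**Working it through.** **The plan's own figures.** The plan gives no hazard ratio. Its failure rates of 25% and 15% imply HR = ln(0.85)/ln(0.75) = 0.565 under proportional hazards. It gives no split of failures before and after 48 hours and no discharge distribution, so those inputs are assumed below.

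**Step 1: set-up.** Control failure is 25% by 168 h (the plan's rate; applying it at 168 h is an assumption). The control hazard λ is constant. Discharge or end of therapy is a competing event with mean 120 h, in two shapes: (A) exponential from time zero; (B) none before 48 h, then exponential with mean 72 h.

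For shape A, with μ = 1/120 per hour, solve λ/(λ+μ) × [1 − exp(−168(λ+μ))] = 0.25. This gives λ = 0.00341 per hour. Control failures are then 0.2904 × (1 − exp(−48 × 0.01174)) = 12.5% by 48 h and 25.0 − 12.5 = 12.5% afterwards.

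**Step 2: three truths.** With HR 0.4 early and 1.0 late in shape A, the adhesive arm fails 5.2% by 48 h and 13.8% later, 19.0% in all. The differences are 12.5 − 5.2 = 7.3 points at 48 h and 25.0 − 19.0 = 6.0 points at 168 h. The other rows follow in the same way. The Cox ratios come from simulated arms of 400,000; ranges cover shapes A and B.

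| True HR before / after 48 h | Cox HR, all from time zero | Cox HR, dwell > 48 h only | Difference at 48 h (points) | Difference at 168 h (points) |
|---|---|---|---|---|
| 0.4 / 1.0 | 0.71 | 1.00 | 7.3 | 6.0–6.2 |
| 1.0 / 0.4 | 0.69 | 0.40 | 0.0 | 7.0–7.2 |
| 0.7 / 0.7 | 0.70 | 0.70 | 3.6 | 6.4–6.6 |

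An event-weighted mean of the log hazard ratios confirms the first row roughly. Early events are 12.5 + 5.2 = 17.7 per 100 per arm and late events 12.5 + 13.8 = 26.3, so exp[(17.7 × ln 0.4)/44.0] = 0.69.

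Neither the blended ratio nor the 168-hour difference separates the three truths. The 48-hour and 168-hour differences together do.

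**Step 3: how far this depends on the assumptions.** Use the plan's implied ratio of 0.565 before 48 h, 1.0 after it, and 30–70% of control failures before 48 h. The blended HR is then 0.87 to 0.70 if everyone is followed to 168 h, and 0.81 to 0.64 with discharge censoring. In simulated trials of 175 per arm with no late benefit at all, the blended test was significant in favour of the adhesive in 10% to 41% of trials.

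**Step 4: the dwell-over-48-hours reading.** In the table this ratio recovers the late effect, but only because all catheters within an arm were given the same risk. Suppose risk varies between catheters as a gamma frailty with variance θ. The ratio among survivors at 48 h is then the true late ratio times (1 + θΛ₀)/(1 + θΛ₁), where Λ is the cumulative hazard to 48 h. With Λ₀ = 0.00341 × 48 = 0.164 and Λ₁ = 0.4 × 0.164 = 0.065, the factor is 1.164/1.065 = 1.09 for θ = 1 and 1.327/1.131 = 1.17 for θ = 2. A true late ratio of 1.0 would look mildly harmful. Both values of θ are illustrative.

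**Step 5: precision.** At the plan's average rate of 20%, 350 patients give 70 failures. If half are late, the SE of the log HR is about 2/√35 = 0.34, and the 95% CI is the estimate multiplied and divided by exp(1.96 × 0.34) = 1.94. With 30–70% of failures early, there are 49 to 21 late failures and the factor is 1.75 to 2.35. Power to detect 0.565 in the late period, Φ(√D × 0.571/2 − 1.96) with D late failures, is 52% to 26%. Power for an early-versus-late interaction (0.565 against 1.0) is about 17–22%.

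**The case against.** A reader might infer that the planned ratio can say nothing about the period after 48 hours. The documents do not support that. Under the Exclusion Criteria sentence every analysed failure falls after 48 hours, and in Step 2 that restricted ratio separated all three truths. What remains is that it compares survivors only, discards early failures, and cannot supply the overall effect in the Study Design section. Appendix E also leaves it unclear whether that sentence governs.

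A reader might also infer that persistence beyond 48 hours is a stated aim. It is not. The rationale asks for a longer period of study, and the aims concern catheter survival overall. A separate late effect is a fair reading of the rationale and no more.

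Nor do the documents say that the adhesive's effect changes with time. The Background names dislodgment and micromotion as causes of failure and gives no timing for either, so non-proportional hazards are a possibility to examine.

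The plan also leaves room for more than one ratio: Aim 1 speaks of estimating catheter survival, and Study Design allows exploratory secondary and adjusted analyses. None of these is specified by period.

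Finally, the near-identical ratios in Step 2 arise partly because the assumptions put about half of control failures before 48 hours, and 0.4 against 1.0 is a stronger contrast than the plan's implied 0.565. Step 3 shows that the blending persists under milder inputs, with a varying size.

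**Conclusion.** The point holds in limited form. Under either inclusion rule, one Cox ratio leaves part of the question unanswered. With early failures kept, it can sit near 0.70 whether the benefit is early only, late only or constant; with no late benefit and an early ratio of 0.565 it ranges from 0.64 to 0.87. With dwell over 48 hours required, it describes the late period among selected catheters and gives no total effect from time zero.

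The sizes rest on an assumed failure time course and discharge pattern that the documents do not give. The conflict between the dwell and discharge rules, and the absence of any period-specific estimate, rest on the text alone. This is worth correcting before analysis; it does not invalidate a Cox test as the main comparison.

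**What to change.** 1. Reconcile the last paragraph of the Exclusion Criteria section with the Appendix E column, including the clock (re-dressing or insertion).
2. Run the Cox test in all randomized catheters from time zero, including those that fail or whose patients leave before 48 hours.
3. Pre-specify the between-arm difference in cumulative incidence of failure at 48 h and at 168 h, each with a 95% CI, with discharge or end of therapy as a competing event.
4. Report Cox hazard ratios for 0–48 h and 48–168 h with CIs as supportive estimates. Read them beside the differences in item 3, because the late ratio is still among survivors.

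The cost is revised wording and a little more analysis, with no extra data collection beyond keeping early discharges in the dataset. The drawback is imprecision: with an SE of the log HR of about 0.35, each period ratio has an interval of roughly two-fold either way. The period ratios should therefore be described as estimates. They are not a powered test and should not be the sole gate for any conclusion about persistence.

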### **Data Collection/Management Plan:**

Data will be collected as subjects are enrolled and information will be stored in a password protected excel file until ready for statistical analysis.

### **Publication and Presentation Plan:**

The publication plan is to submit a manuscript to a high impact medical journal. This publication has the potential to significantly change securement practice and enhance quality for patients. The study results will also be presented at least one national meeting and potentially additional vascular access conferences.

### **Potential Impact:**

Optimization of peripheral vascular care is a critical strategy to improve patient outcomes and reduce health care costs. Enhanced dwell times will lead to improved patient/staff satisfaction, decreased interruptions in care with shorter hospital length of stay, and decrease in complications such as thrombosis, bleeding, and infection. At the Royal Oak campus, over 450,000 IV catheters are purchased annually. Across the health system, this number exceeds 2 million catheters per year. In a study by Rickard et al in 2012, a patient required an average of 1.7 IV catheters per admission. With a cost of approximately \$35 per catheter for straightforward insertions, even a slight improvement in dwell time has the potential to save our health system millions of dollars.

## Appendix A: Standard Dressings with Securement

[figure not shown]
[figure not shown]
06.15.2020

IRB NUMBER: 2019-188  
IRB APPROVAL DATE: 06/16/2020

## Appendix B: Tissue Adhesive Application Instructions

|  |  |
|--|--|
| 
Point the tip towards the ceiling and away from the patient. Press the bottom of the applicator upward.
   |  |
| 
Invert the applicator and gently squeeze the ridges to initiate adhesive flow. Place 1-2 drops of adhesive at the catheter-skin junction.
 
Allow each drop of glue to “set-up” for a few seconds before adding the next drop.
 
Make sure the tissue adhesive is surrounding the entire circumference of the catheter.
 |  |
| 
Place an additional 1-2 drops of adhesive under the catheter hub/extension set connection.
 
Apply gentle pressure for 30 seconds to ensure securement between the catheter and the skin surface.
  |  |

|  |   |
|--|---|
| 
As desired, the remaining adhesive can be spread out beyond the area of the catheter to increase dressing adherence.
 |  |
| 
After application of SecurePortIV, a transparent film dressing should be applied per facility protocol.
                     |  |

### **Appendix C: Signs and Symptoms of Catheter-Related Complications**

- 
- 1. Any level of pain and/or tenderness with or without palpation**
  - 2. Changes in color (erythema or blanching)**
  - 3. Changes in skin temperature (hot or cold)**
  - 4. Edema**
  - 5. Induration**
  - 6. Leakage of fluid or purulent drainage from the puncture site**
  - 7. Other dysfunction (e.g. resistance with flushing, lack of blood return)**
- 

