**Study Procedure:**

***Initial Assessment:***

Patients admitted from the ED to a progressive floor are eligible participants. Research staff will approach a convenience sample of patients admitted to the progressive floors based on screening of the electronic medical record. These patients are admitted to a progressive floor but approached by research staff when physically in the emergency department waiting for a room assignment. The principal investigator may also choose to include additional patients admitted to non-progressive inpatient units. The principal investigator will inform the research staff when such cases arise. Similar to other study subjects, these patients will be approached in the Emergency Department. If the patient agrees to participate in the

trial, the study subject will be consented by the research staff. Research staff will confirm functionality of the existing IV previously placed by ED staff. The assessment will include observing for blood return into the tubing upon aspiration and/or unobstructed flush with a minimum of 1-2 ml of normal saline. Staff will also observe the site for any signs of redness or tenderness.

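### A skin reaction to the adhesive is not separately recorded or analysed: its signs are logged as catheter complications, and the only removal code open to it besides the catheter causes is 'other'

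*Combined protocol and SAP*

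**What the plan says.** - **Anticipated reaction.** The Exclusion Criteria list "Known allergy to cyanoacrylate or formaldehyde".
- **Baseline.** Under Initial Assessment, before randomization and so before any adhesive is applied: "Staff will also observe the site for any signs of redness or tenderness". Patients are randomized if the catheter works and shows no sign of a complication.
- **Follow-up.** Visits are every 24 +/- 5 hours, up to 168 hours. "Catheters will be assessed daily for signs and symptoms of complications", with Appendix C as the guide. Findings are documented with date and time and passed to the treating team. If the catheter came out between visits, the reason is taken from the chart. On taking the adhesive off, the section says only that "a medical adhesive remover may be used".
- **Appendix C.** Seven signs, all under a title that calls them catheter-related. They include "Any level of pain and/or tenderness with or without palpation" and "Changes in color (erythema or blanching", and also temperature change, edema and induration.
- **Appendix E.** A daily row with an open column for signs and symptoms, and ten removal reasons. Code 3 is phlebitis, and the list ends "8) removed by patient (9) site changed (10) other".
- **Aim 2.** "Specific etiologies to be evaluated include dislodgment, infection, phlebitis, and occlusion".
- **Statistical Analysis.** Cox models for time-to-event outcomes and logistic models for binary outcomes, applied to the aims. No safety or skin outcome is named.

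**The concern.** The two arms differ by one product, applied to the skin. Pain, redness, swelling and hardening at the site can come from the catheter or from what is stuck around it, and the forms do not separate the two. Two things follow.

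First, the trial could report on catheter failure, with the stated hope of changing securement practice, and have no count of skin reactions by arm to set beside that result.

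Second, a removal prompted by a reaction has to go under an existing code. If staff choose phlebitis, a cause that Aim 2 compares between arms takes in events of a different kind. If they choose 'other', the reaction is mixed with every other unlisted reason and cannot be counted without free text.

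**Working it through.** The plan states no figure on this point, so the check is to follow a reaction through the documents.

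1. **Could it be seen?** Yes, while the catheter is in place and a visit falls due. The Appendix C signs cover what a local reaction would produce, in both arms.
2. **Could it be recorded as a reaction?** Not by any defined item. The sign is written down as a catheter-related complication. The open column could hold a note, but nothing asks for cause or for whether the finding lies under the adhesive.
3. **If it leads to removal, how is it coded?** Codes 2 to 7 are infiltration, phlebitis, dislodgement, oozing, purulent drainage and occlusion. Code 1 is completed therapy, and codes 8 to 10 are removal by the patient, site change and 'other'. None is for skin. Phlebitis and 'other' are the likely choices, and no instruction decides between them.
4. **If it appears when the adhesive is taken off?** No skin check at that moment is stated, and the form has no field for it. For removals between visits the chart is the only source.
5. **Is it analysed?** Aim 2 names four causes, none of them skin reaction. The analysis section adds no table by arm. In addition, the Exclusion Criteria section limits the survival analysis to dwell times over 48 hours, so a reaction that ends the catheter's use sooner does not enter that analysis.

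**Can the effect be sized?** Only by assumption. The sample size section gives 175 per group and failure rates of 25% and 15%, so the expected failures are 175 x 0.25 = 43.75 (control) and 175 x 0.15 = 26.25 (adhesive). These use all enrolled patients and ignore dropout and the 48-hour restriction.

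- *Reaction rate, assumed 1% to 5%:* 175 x 0.01 = 1.75 and 175 x 0.05 = 8.75, or about 2 to 9 patients.
- *Equal split over Aim 2's four causes (assumed):* 43.75/4 = 10.9 against 26.25/4 = 6.6. Two extra adhesive-arm cases coded as phlebitis give 8.6 and four give 10.6. The difference shrinks but does not reverse.
- *Equal split over codes 2 to 7 (assumed):* 43.75/6 = 7.3 against 26.25/6 = 4.4. Three extra cases give 7.4, which removes the difference. Four give 8.4, which reverses it.

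The answer changes with the assumed split, and the documents supply neither the split nor the rate, nor the share of reactions that would lead to removal.

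**The case against.** The strongest reply is that the plan already captures most of this. The site is examined about daily in both arms, the signs are written down with date and time, the treating team is told, and code 10 and the open column can take a reaction. Signs could be tabulated by arm from the existing form. All of that stands, and it rules out several stronger readings that a reader might infer:

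- *There is no skin check.* There is one about daily. What is not stated is a check at removal, or any step that separates skin reaction from catheter complication.
- *The plan anticipates toxicity.* The text supports anticipated allergy only. The remark about avoiding skin injury under Initial Assessment is in the control-arm instructions and concerns taking off the existing polyurethane dressing. The remover is an aid to removal, not a stated hazard.
- *Harm goes unreported.* Signs are documented and passed on. Some pages of the document were not available, so the absence of a safety section from the full protocol cannot be shown.
- *Phlebitis in the adhesive arm will be inflated.* It may be, but if staff use 'other' it is not. Both arms also have dressing and tape, and a reaction to those is equally uncoded.
- *Up to a third of adhesive-arm failures could be reactions* (8.75/26.25 = 33%). That needs an assumed 5% rate and every reaction to cause removal.
- *The primary result is biased.* A sign is not by itself an Aim 1 event. Aim 1 uses loss of function, and the sample size section uses premature removal for a complication.

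The reply does not answer the rest: nothing directs staff to use code 10 or the open column for this, and no comparison by arm is planned in the available text.

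**Conclusion.** The point holds as a gap in recording and analysis. The plan foresees a reaction to the adhesive and would probably see its signs, but as written it does not record a reaction as such, states no skin check at removal, and plans no skin outcome by arm in the available text. A reaction that leads to removal may be coded as phlebitis or as 'other'. Its frequency and its effect on Aim 2 cannot be sized from the documents. The illustrative counts show only that the effect could range from small to enough to reverse one cause-specific comparison, depending on assumptions the plan does not settle. The Aim 1 conclusion is not called into question by this point. It is a cheap improvement, not a flaw that undermines the trial.

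**What to change.** In Appendix E, for both arms:

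1. Add a removal reason, *skin reaction or injury under dressing/adhesive*, separate from phlebitis.
2. Add a yes/no skin finding at the existing daily check and at removal, taken from the chart when ward staff remove the catheter.
3. In the analysis section, plan a descriptive table of both items by arm as a safety outcome. It should not be limited to dwell times over 48 hours, or early reactions would be lost from it.
4. Leave the counting of failures for Aim 1 unchanged.
5. In Aim 2, report phlebitis twice: with and without the cases given the new code.

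The cost is one code, one tick-box on a form already filled in at each visit, and one table. There are two drawbacks. Telling a skin reaction from early phlebitis is a judgement by staff who can see the adhesive, and it could move true phlebitis out of the adhesive arm's count and so favour the product; the two-way report in item 5 is there to show this. Chart entries at removal may also be incomplete, so the number of removals with no skin entry should be shown by arm.
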